#### Organ Implantation prior to Reperfusion

At the time of transplant, the first donor lung will be flushed with a cold pneumoplegia solution after the bronchial (1st) anastomosis. The pneumoplegia solution used clinically at UPMC is a 50% Dextrose/autologous blood preparation, which includes Nitroglycerine, Verapamil and Heparin (refer to Appendix C for description of UPMC pneumoplegia solution); and the Sodium Nitrite will be added just prior to use. A second flush of pneumoplegia solution will occur after the PV (3rd, last) anastomosis. The identical pneumoplegia solution as outlined above will be used for the second flush, but at a temperature range of 34- 38 °C. The same process of flushing with pneumoplegia solution will be followed for the second donor lung.

To the recipient at the time of reperfusion:

Sodium Nitrite will be delivered intravenously to the recipient *immediately* prior to the first lung reperfusion as a single infusion of Infuse at 4 mL/min for the first 30 min, followed by 2.2 mL/min for the next 60 min.

#### 5.6 **Dosing Adjustments and/or Discontinuation due to Adverse Events**

The Sodium Nitrite infusion will only be initiated if the patient's mean arterial pressure (MAP) > 50 mm Hg. The patient's blood pressure may be supported by vasoactive medications and/or volume resuscitation at the time of study drug infusion as directed by the patient's clinical involved anesthesiologist.

If the patient meets criteria for initiation of the study medication, the infusion will be started at the prescribed rate and continue as outlined above. The pre-infusion MAP will be established by the treating anesthesiologist. The study medication will continue unless the patient's MAP falls > 20% compared to the recorded baseline at the start of the study drug infusion. A fall in MAP > 20% will result in the study drug being stopped for 10 minutes and the patient's MAP will be continuously monitored.

If the MAP returns to within 10% of the MAP baseline determined prior to study drug infusion, the infusion may be restarted after a 10 minute interval. This transient fall in MAP with rapid reversal will be attributed to the study drug. If the MAP falls again to > 20% from the MAP baseline, the cycle may be repeated for a maximum of two intervals. The patient's MAP must return to within 10% of the baseline before any restart of the study medication.

If the MAP fails to return to within 10% of the MAP baseline determined prior to study drug infusion, the infusion will be suspended pending hemodynamic resuscitation as directed by the staff anesthesiologist. A more prolonged period of hypotension suggests the effects of organ reperfusion rather than study medication but the infusion will be held to allow stabilization of the patient. The study drug infusion will be restarted once the patient's MAP returns to within 10% of the baseline value.

The study medication may be infused up to 1 hour following the organ reperfusion if hemodynamic stability is delayed.

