#### 2.4 Endpoints

#### Primary Endpoints Analysis

- The primary endpoint for the safety of Sodium Nitrite administration will be assessed by measurement of methemoglobin levels and mean arterial pressure during the nitrite infusion in the transplant recipient.
- The primary endpoint for the efficacy of Sodium Nitrite infusion will be the incidence of grades 2 and 3 PGD using the International Society for Heart and lung transplant (ISHLT) criteria for PGD based upon the worst value obtained over the initial 72 hours post lung reperfusion (T0-72).

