#### 5.7.2 Study monitoring

#### 1) Required end points during study drug infusion

• Mean Arterial Pressure:

The recipient's mean arterial pressure (MAP) will be monitored at 1 minute intervals during study drug infusion followed by 15 minute intervals for 1 hour.

• Nitrite and metabolite levels:

Blood samples will be obtained prior to the infusion; at 5, 30, and 60 minutes during the infusion; and at 5, 10, 30, 60, 90, 150 after the infusion to measure plasma and whole blood nitrite, plasma nitrate, red cell iron-nitrosyl-hemoglobin, S-nitroso-hemoglobin and methemoglobin concentrations. However, no sample will be sent for methemoglobin concentration prior to drug infusion. Blood samples will also be obtained every 24 hours for two days for future exploratory biomarker/proteomic studies which would include evaluation of IL6, IL $\beta$ , TNF-a, iNOS and COX-2. Nitrite levels will be measured by established methodologies (ozone-based reductive chemiluminescence) routinely performed in [name] NO Metabolomics Core facility.

2) Required end points post study drug infusion to hospital discharge

Following administration of the Sodium Nitrite, the study subjects will continue to receive usual care for their condition consistent with local transplant treatment protocols. The study will not introduce any modification to the normal care algorithms. Day 0 ( $D_0$ ) will be defined as the day of transplantation and reperfusion. Subsequent study days will be numbered sequentially. The following parameters will be required for collection prospectively. They will be obtained specifically for the study protocol if not requested by the treating physician. If requested by the treating physician the parameters will be recorded from the medical record. Specific parameters required to be monitored following lung transplantation/reperfusion will include:

• Arterial blood gas measurements from D0 to D3

The  $Pa0_2/FiO_2$  ratio and oxygenation index will be calculated based upon an arterial blood gas at D0 (within 6 hours of reperfusion), and D1, D2, and D3. The initial measurement (D0) will be obtained on a FiO2 of 1.0 and PEEP of 5 while on mechanical ventilation. Subsequent measurements will be obtained on the prescribed ventilator settings. Ventilator parameters will be obtained with each blood gas determination. **There will be no arterial blood gas measurement on days patient is extubated.** 

• Chest radiography from D0 to D3

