## 5.7.3 Optional end points to be obtained from admission to ICU discharge based on standard clinical monitoring

#### (1) Arterial blood gas measurements from D4 to ICU discharge

The Pa02/FiO2 ratio and oxygenation index will be calculated and the worst value for each individual day recorded for analysis. Corresponding ventilator parameters will be recorded.

(2) Plain film portable chest radiography from D4 to ICU discharge

All chest radiography will be referred to a radiology core for independent review and classification independent of the review required for clinical documentation.

(3) Requirement for extracorporeal support and days

Any day beyond  $D_0$  to ICU discharge in which the patient receives extracorporeal support will be counted.

(4) Requirement for inhaled NO support and days

Any day beyond  $D_0$  to ICU discharge in which the patient receives inhaled NO support will be counted.

- Results of Echocardiography -specifically the left ventricular function and estimated pulmonary arterial pressure (PA systolic, PA diastolic, and mean) to evaluate cardiac and pulmonary arterial function.
- D0 to ICU discharge
  - ventilator settings
  - -vital signs
  - 24 hour fluid balance

- hemodynamic indices including MAP, PA pressures, central venous pressures, cardiac index.

- 3) Additional end points to one year post hospital discharge obtained only if needed for patient's standard care
  - Results of pulmonary function tests specifically the FVC, FEV1, and FEV1/FVC ratio.
  - Lung Biopsy Results specifically the diagnosis of acute cellular rejection and grade, bronchiolitis obliterans (BO), and treatment.
  - Complications including major opportunistic infections and subsequent hospitalizations.

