#### 5.8 Safety Assessment

The primary safety assessment will be based upon measured methemoglobin levels and hemodynamic indices during the Sodium Nitrite infusion. Because of the exploratory nature of this trial, all potential Adverse Events will be recorded for review.

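### MAP during the infusion is a primary safety endpoint, but blood-pressure support given over the same period is not collected, so a small or absent MAP fall cannot be interpreted

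*Combined protocol and SAP*

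**What the plan says.** Under Primary Endpoints Analysis, section 2.4 assesses safety by "measurement of methemoglobin levels and mean arterial pressure during the nitrite infusion in the transplant recipient". Section 5.8 is worded more widely: "The primary safety assessment will be based upon measured methemoglobin levels and hemodynamic indices during the Sodium Nitrite infusion". It does not say which indices are meant.

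Section 5.6 deals with blood pressure during the same infusion:

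- "The patient's blood pressure may be supported by vasoactive medications and/or volume resuscitation at the time of study drug infusion", as the anesthesiologist directs. There is no limit on support and no rule to keep it constant.
- "The pre-infusion MAP will be established by the treating anesthesiologist". The level of support at that moment is not requested.
- "The study medication will continue unless the patient's MAP falls > 20% compared to the recorded baseline". This is a rule for holding the drug; no MAP event is defined as an endpoint.
- A brief fall that reverses quickly is ascribed to the drug, whereas "A more prolonged period of hypotension suggests the effects of organ reperfusion rather than study medication".

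Section 5.7.2 lists the data required around the infusion: "mean arterial pressure (MAP) will be monitored at 1 minute intervals during study drug infusion", then every 15 minutes for an hour, plus nitrite, its metabolites and methemoglobin. The optional list in 5.7.3 has "hemodynamic indices including MAP, PA pressures, central venous pressures, cardiac index", with vital signs, ventilator settings and a 24-hour fluid balance. The study has one non-randomized cohort of 8 (5.1, 5.7.1). The historical controls in 5.9 serve the PGD comparison.

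**The concern.** When a clinician may adjust drugs and fluids to support pressure, MAP is at least partly a controlled quantity. A vasodilator effect can then appear as a fall in MAP, as more support, or as some of each. The plan records the first and not the second.

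This matters because hypotension is one of the two adverse events that section 10.3 expects most often from the intervention, and section 8.1 says safety in lung transplant recipients has not been established. The infusion starts immediately before reperfusion (5.5), a time at which section 5.6 itself expects hypotension and resuscitation. The Abstract says positive results should lead to a larger trial, so a MAP result that cannot be interpreted would be carried forward.

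**Working it through.** The plan states no event rate, margin, power or analysis for MAP, so there is no figure to reproduce. The main check is of the text; steps 3 to 5 are illustrations with assumed inputs.

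**1. Where could support be captured?**

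- 5.7.2, required infusion data: MAP and nitrite-related levels; no vasoactive dose, no fluids.
- 5.7.3, optional data: no vasoactive dose; fluids only as a 24-hour balance, which cannot isolate the infusion.
- SOFA (5.7.2), which has a cardiovascular component: begins on D1. The infusion is on D0.
- 5.8: unspecified hemodynamic indices.
- Section 6: no analysis of MAP that takes account of support.
- Adverse event rules (5.8, 10.5.2): an abnormal finding that needs significant added drug treatment counts as an adverse event. This can reach hypotension that was seen and treated, but not systematically support that kept MAP from becoming abnormal.

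**2. Size of the record.** The infusion lasts 30 + 60 = 90 minutes if uninterrupted. One-minute readings give about 90 values, and the following hour gives 60/15 = 4. That is about 94 per patient and 8 × 94 = 752 in all. The number of required support values to set beside them is zero.

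**3. One patient.** Let B be baseline MAP, d the fall under constant support and s the pressure restored by added support, all in mm Hg and all assumed. Observed fall = (d − s)/B.

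| B | d | s | Fall, constant support | Observed fall |
|---|---|---|---|---|
| 75 | 18.75 | 5 | 25.0% | 13.75/75 = 18.3% |
| 70 | 20 | 10 | 28.6% | 10/70 = 14.3% |
| 60 | 15 | 5 | 25.0% | 10/60 = 16.7% |

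In each row the observed fall is below 20%, the only MAP threshold in the plan. In the first row MAP reads 61.25 instead of 56.25. This requires support to keep pace with the drug effect; if MAP reached 56 first, a one-minute reading would probably show it.

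**4. Eight patients.** Let p be the assumed share who would fall by more than 20% under constant support, and m the assumed share of those falls masked. P(none of 8 shows a fall > 20%) = (1 − p(1 − m))^8.

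| p | m = 0 | m = 0.5 | m = 0.75 |
|---|---|---|---|
| 0.40 | 0.60^8 = 1.7% | 0.80^8 = 16.8% | 0.90^8 = 43.0% |
| 0.20 | 0.80^8 = 16.8% | 0.90^8 = 43.0% | 0.95^8 = 66.3% |

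A true share of 0.40 with half masked gives the same result as 0.20 with none masked. MAP alone informs only the product p(1 − m).

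**5. What 0 of 8 would show.** The one-sided exact 95% upper bound is 1 − 0.05^(1/8) = 31.2% (36.9% two-sided). That bounds p(1 − m). With m = 0.5, the one-sided bound on p is 0.312/0.5, about 62%.

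**6. Attribution.** Section 5.6 judges cause by speed of recovery, and support affects that speed. A reperfusion-related fall reversed quickly by a bolus would be charged to the drug. A drug-related fall that recovers slowly would be put down to reperfusion. Without support data neither misattribution can be recognized.

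**The case against.** The strongest reply is that the plan is exploratory and section 6 disclaims firm conclusions, while several provisions already reach hypotension. One-minute MAP catches a dip that precedes the response to it. Section 5.8 records all potential adverse events, section 10.5.2 records them whatever the suspected cause, coordinators review records until 72 hours after the last dose (10.2), and hypotension is reported to the sponsor (10.3). Section 5.8 also speaks of hemodynamic indices, which is broader than MAP. Further, the permission for support follows directly on the MAP condition for starting the drug, so it may mainly allow patients already on support to begin; active titration to hold MAP is an inference. The anesthesia record probably contains the doses anyway.

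Much of this stands and narrows the point. Treated hypotension does have a route into the safety data. Support raised before an abnormal reading has none, support at baseline is not requested, and an undefined reference to indices requires nobody to collect doses. A record that probably exists is not yet study data.

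Three stronger readings are tempting and not supported:

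- A reader might infer that the plan would score a masked effect as no effect and declare hemodynamic safety. It has no scoring rule for MAP; the 20% fall governs holding the drug.
- A reader might infer that the error always favours the drug. Masking of a fall does, but the attribution rule can err either way.
- A reader might infer that a merged primary event, a MAP fall or any increase in support, is needed. Around reperfusion, with 8 patients and no control, it could mark most patients regardless of the drug.

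**Conclusion.** The point holds as a gap in data capture and reporting for a primary safety endpoint. Followed as written, the plan yields MAP records in which no effect and a partly offset effect look alike. This rests on the text: support is permitted, it need not be constant, its dose is in neither data list, and there is no concurrent control.

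The size cannot be fixed from the documents, which do not say how many recipients receive support or how it is adjusted. The figures in steps 3 to 5 show how masking works; they are not estimates for this trial. If one assumed that 50% to 100% of recipients receive titrated support, 4 to 8 of the 8 MAP records would be open to masking, but that only restates the assumption. Nor do the documents support saying that the trial cannot address its hemodynamic question at all: sharp falls would still be seen and treated episodes partly reported. The change is worth making because it is cheap and the data cannot otherwise be read.

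**What to change.** Change data and analysis only, leaving patient care and the hold and restart rules as they are.

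1. In 5.7.2, require abstraction from the anesthesia record of vasopressor and inotrope doses and boluses, and of fluid boluses, at the pre-infusion baseline, through the infusion and for the following hour. This matches the window in which MAP is already collected.
2. In the safety analysis, report for each patient the MAP change together with the change in support. List MAP falls > 20% and increases in support as separate descriptive components.
3. For each recovery of MAP after a fall, note whether it occurred with added support.

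The cost is a little abstraction work in 8 patients and a few sentences in the plan. Some increases in support will reflect reperfusion rather than the drug, and the added data will not by themselves separate the two. For that reason the components should be shown side by side and not merged into one primary event.

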#### Organ Reperfusion to Recipient

A specifically labeled frozen syringe of prepared stock Sodium Nitrite solution (1.33 mL, 30 mg/,L) will used by the UPMC pharmacy to prepare a 40 mg Sodium Nitrite in a 250 ML infusion

bag of normal saline (i.e., 0.16 mg/mL) The entire volume of this bag will be used to administer to the patient at the time of Organ Perfusion.

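### Section 5.6 requires MAP above 50 mm Hg to start the infusion but sets no absolute limit for continuing or restarting it, so drug may run at pressures that would bar a start

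*Combined protocol and SAP*

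**What the plan says.** Section 5.6 contains four rules on blood pressure.

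- **Start.** "The Sodium Nitrite infusion will only be initiated if" MAP exceeds 50 mm Hg. The treating anesthesiologist sets the pre-infusion baseline, and "blood pressure may be supported by vasoactive medications and/or volume resuscitation at the time of study drug infusion".
- **Continue.** The infusion runs unless "MAP falls > 20% compared to the recorded baseline at the start of the study drug infusion". A larger fall stops the drug for 10 minutes.
- **Restart after a short hold.** If MAP recovers, the drug may be resumed, and "the cycle may be repeated for a maximum of two intervals". The general condition is that "MAP must return to within 10% of the baseline before any restart of the study medication".
- **Restart after a prolonged hold.** If MAP does not recover, the infusion is suspended during resuscitation. "The study drug infusion will be restarted once" MAP is again within 10% of baseline. On cause, the section says: "A more prolonged period of hypotension suggests the effects of organ reperfusion rather than study medication".

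The section closes by allowing infusion for up to 1 hour after reperfusion when stability is delayed. MAP is read every minute during infusion (section 5.7.2) and, with methemoglobin, is the primary safety endpoint (section 2.4).

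**The concern.** The 50 mm Hg figure is the only absolute MAP limit in the plan, and it acts once, at the start. A patient whose baseline lies only a little above 50 can then receive drug at pressures well below the value the protocol itself treats as too low to begin. No reason is given for the difference.

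Hypotension is one of the two adverse events the protocol most expects (section 10.3). Section 8.1 acknowledges that nitrite's safety in lung transplant recipients has not been established. The infusion also begins immediately before the first lung is reperfused (section 5.5), and section 5.6 itself links reperfusion with hypotension. What is at stake is a safeguard during dosing. The MAP data and the recording of adverse events are not affected.

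**Working it through.** **Inputs, all from section 5.6.** Start limit: MAP > 50 mm Hg. Stop: a fall of more than 20% from baseline B. Restart: within 10% of B. The plan states no derived figure to reproduce.

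**Formulas.**
- Lowest MAP at which infusion continues = 0.8 × B
- Lowest MAP at which restart is allowed = 0.9 × B
- Percentage fall that brings MAP to 50 = 1 − 50/B

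| Baseline B (mm Hg) | Continues down to | May restart at | Fall that reaches 50 |
|---|---|---|---|
| 51 | 40.8 | 45.9 | 2.0% |
| 52 | 41.6 | 46.8 | 3.8% |
| 55 | 44.0 | 49.5 | 9.1% |
| 60 | 48.0 | 54.0 | 16.7% |
| 62.5 | 50.0 | 56.25 | 20.0% |
| 65 | 52.0 | 58.5 | 23.1% |

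**Baselines affected.**
- Continuation: 0.8 × B ≤ 50 when B ≤ 50/0.8 = 62.5.
- Restart: 0.9 × B ≤ 50 when B ≤ 50/0.9 = 55.6.
- Both ranges begin just above 50, because a patient at or below 50 cannot start.

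**Largest shortfall below 50.** As B approaches 50 from above, the continue limit approaches 0.8 × 50 = 40 and the restart limit approaches 0.9 × 50 = 45. The shortfall is therefore just under 10 mm Hg while continuing and just under 5 mm Hg at restart.

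**Does another section close the gap?** The monitoring section (5.7.2), the safety assessment (5.8) and the monitoring plan (10.1 to 10.4) set no MAP limit during infusion. The systolic limit of 90 mm Hg in section 7.1.4 is a pre-operative exclusion. Reading the start rule as covering restarts does not help: restarting has its own criterion, and continuation would still have no absolute limit.

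**The case against.** **A start limit and a stop rule may differ.** This is the strongest objection. Once drug is running, a relative fall can be the better signal of a drug effect, and an absolute stop at 50 works poorly just above 50. At a baseline of 51, a 2.0% fall would stop the infusion, and with readings every minute ordinary variation could do that. This stands, and it is why the stop limit is left to the team. It does not reach restart. Resuming drug after a hypotensive stop is a fresh decision to give it, and no reason is offered for accepting a lower pressure than at the first start.

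**Exposure is limited.** An anesthesiologist is present, may support pressure and directs resuscitation. Section 7.1.4 excludes several cardiac and hemodynamic risks, and only 8 patients are planned. All of this reduces the likely harm, but none of it sets a limit.

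**Stronger readings that the documents do not support.**
- A reader might infer that the affected patients are the frailest. Nothing shows that an intra-operative MAP of 51 to 62 marks such patients, and the exclusions in section 7.1.4 point the other way.
- A reader might use the 42-minute plasma half-life in section 8.1 to argue that prolonged hypotension is a drug effect. That figure describes plasma nitrite. The documents do not relate concentration to MAP or give the duration of the MAP effect.
- A reader might conclude that restarts after a prolonged hold are unbounded, since the two-interval maximum is stated only for the short-hold path. The 1-hour allowance after reperfusion reads as a time limit for delayed stability. The dose is also bounded, because "The entire volume of this bag will be used to administer to the patient" and the bag holds 250 mL × 0.16 mg/mL = 40 mg.
- A reader might fear that the sentence on reperfusion removes long episodes from the safety record. It is not binding, and the drug is held anyway. All potential adverse events are recorded (section 5.8), and hypotension is reported to the sponsor with no condition on duration (section 10.3). Under section 10.5.2, a test finding that changes dosing is an adverse event, and events of unknown and questionable relationship count as drug-associated.

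**Conclusion.** The gap is real and minor. Section 5.6 permits restart at or below 50 mm Hg for baselines above 50 and up to about 55.6, and continuation at or below 50 for baselines above 50 and up to 62.5. The arithmetic assumes only that the 20% and 10% rules mean 0.8 and 0.9 times the recorded baseline. No baseline MAP distribution is given, so how many of the 8 patients would be affected cannot be estimated and could be none.

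The case is firm for restart. For continuation, the firm conclusion is that an absolute limit should be stated; whether it should be 50 is a clinical judgment. The sentence attributing prolonged hypotension to reperfusion has no data or citation behind it. That makes it unsupported, not wrong, and it has little practical effect.

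**What to change.** 1. **Restart.** Require MAP above 50 mm Hg, in addition to the within-10% rule, before any restart, after a short or a prolonged hold.
2. **Continue.** Add an absolute MAP stop limit during infusion, alongside the 20% rule. Use 50 mm Hg, or a lower value with a stated reason. A value of 40 or below would add nothing, since 0.8 × B is always above 40 when B is above 50. State whether a stop triggered by this limit counts toward the two-interval maximum, so that small dips at low baselines do not end dosing unintentionally.
3. **Optional.** Delete the sentence attributing prolonged hypotension to reperfusion but keep the hold, and count every fall of more than 20% in the safety summary whatever its duration.

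**Cost.** Wording only; the minute-by-minute MAP readings already exist. The restart rule becomes tighter at low baselines: at 51, MAP must recover to within 2.0% of baseline instead of 10%. Some of these patients will have delayed or incomplete 40 mg doses, and a stop limit of 50 would add interruptions. The restart change has no effect above about 55.6, and nothing in items 1 and 2 changes dosing above 62.5.

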The sponsor of this IND application, [name], has previously held an IND for sodium nitrite (IND # 70,411) for cardiovascular applications. The cardiovascular IND involved the administration of Sodium Nitrite to 69 normal volunteers in 4 phase I-II clinical trials without observed adverse effects. We have also treated 11 subjects with sickle cell disease on this IND without observed adverse effects. The low doses of nitrite used in these investigational treatment regimens – approximately 40 mg or 13% of the dose (300mg) used in the emergency treatment of cyanide poisoning – do not produce methemoglobin levels greater than 3% and have not been associated with clinically significant hypotension. There have been no adverse events noted in the 80 treated normal human volunteers and patients with sickle cell disease. While the safety of nitrite in lung transplant recipients has not been established, the short plasma half-life (T1/2 = 42 mins ) and dose chosen for this study minimize the risk of subjects experiencing the known effects of nitrite, specifically methemoglobinemia and hypotension.

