#### 10.3 Parameters to be Monitored

The Clinical Investigator will evaluate any changes in laboratory values and physical signs, and will determine if the change is clinically important, and different from what is expected in the clinical course of patients following a lung transplant. Expected events for lung transplant patients are untoward clinical occurrences that are perceived by the clinical investigator to occur with reasonable frequency in the day to day care of patients with a lung transplant, treated in the hospital setting. Examples of adverse events that are expected in the course of lung transplant care include infection, rejection, and organ failures. Such events will not be considered reportable adverse events unless the event is considered by the clinical investigator to be associated with the study drug or experimental procedures, or is unexpectedly severe or infrequent for a patient undergoing lung transplantation.

An event will be considered to be study drug- or experimental procedure-related if the event follows a reasonable, temporal sequence from the study drug/procedure, and could readily have been produced by the study drug/procedure. An event will be considered to be unexpected for the study drug if it is not identified as a potential adverse event in this clinical protocol, or is unexpectedly severe, or occurs more frequent than events described herein. The most common adverse events expected for this intervention would be hypotension and methemoglobinemia. These events will be reported to the Sponsor of the IND, [name] within 5 days of the event.

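### Section 5.6 separates drug from reperfusion by how long a MAP fall lasts, which the rest of the protocol does not support, and caps restarts on only one of its two routes

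*Combined protocol and SAP*

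**What the plan says.** Section 5.6 handles a MAP fall of more than 20% from the pre-infusion baseline by stopping the drug for 10 minutes. Two routes follow.

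- **Quick recovery.** If MAP is back within 10% of baseline, the infusion may be restarted. On cause: "This transient fall in MAP with rapid reversal will be attributed to the study drug". For further falls, "the cycle may be repeated for a maximum of two intervals".
- **Slow recovery.** If MAP does not come back, the infusion is suspended while the anesthesiologist resuscitates. On cause: "A more prolonged period of hypotension suggests the effects of organ reperfusion rather than study medication". On restarting: "The study drug infusion will be restarted once the patient's MAP returns to within 10% of the baseline value". No maximum number is given.

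The same section allows hemodynamic support throughout: "The patient's blood pressure may be supported by vasoactive medications and/or volume resuscitation at the time of study drug infusion". It also lets drug run up to 1 hour after reperfusion if stability is delayed.

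Other sections bear on cause. Section 8.1 gives the elimination rate ("the short plasma half-life (T1/2 = 42 mins"). Section 10.3 sets a general test, "An event will be considered to be study drug- or experimental procedure-related if the event follows a reasonable, temporal sequence from the study drug/procedure", with the further condition that the drug could readily have caused the event. It adds: "The most common adverse events expected for this intervention would be hypotension and methemoglobinemia". Section 10.5.2 treats an event of unknown and questionable relationship as drug-associated for reporting.

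**The concern.** MAP during the infusion is one of the two measures in the primary safety endpoint (Section 2.4). There are 8 subjects and no concurrent control. Section 5.5 starts the infusion immediately before the first lung is reperfused, so the two candidate causes of hypotension overlap by design and timing alone cannot separate them.

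Section 5.6 separates them by speed of recovery. If drug-caused falls tend to outlast 10 minutes, the rule steers the longer drug effects toward reperfusion. Those falls also go down the route that has no count limit on re-exposure. At stake are how causality is classified in a small safety study, and whether two subjects with similar falls are restarted under the same rule.

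**Working it through.** The plan gives no calculation behind the 10-minute hold, so there is no stated figure to reproduce. The check asks whether a drug-caused fall should be expected to reverse within the hold.

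**Inputs.** Half-life 42 minutes (Section 8.1); hold 10 minutes, stop threshold 20%, restart threshold 10% (Section 5.6); 8 subjects (Section 5.1). The relation between nitrite level and MAP is not given and has to be assumed.

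**1. Drug remaining after the hold.** With first-order elimination, k = ln 2 / 42 = 0.0165 per minute. Fraction remaining = 2^(−10/42) = 0.848. About 15% has gone and 85% is still there, at whatever point the infusion was stopped.

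**2. Recovery time if the effect is proportional to level (assumption).**
- A 20% fall is still 20 × 0.848 = 17.0% at 10 minutes.
- It returns to 10% after 42 × log2(20/10) = 42 minutes.
- A 30% fall needs 42 × log2(30/10) = 66.6 minutes.

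**3. Sensitivity to that assumption.** If the effect varies as level to the power g, a 20% fall reaches 10% in 42/g minutes:
- g = 1: 42 minutes
- g = 2: 21 minutes
- g = 3: 14 minutes
- g = 4.2: 10 minutes

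Put another way, the effect half-life would have to be 10 minutes or less. If fast redistribution did the work with g = 1, the fraction f lost that way must satisfy (1 − f) × 0.848 = 0.5, so f = 0.41.

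**4. Support during the infusion.** Pressors and fluids shorten recovery from either cause. A drug-caused fall treated promptly moves back into the drug category, and a treated reperfusion fall can be credited to the drug. Recovery time is thus a poor discriminator in both directions, and the net direction of error cannot be derived from the documents.

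**5. Section 5.6 against Section 10.** Section 10.3 uses timing and plausibility, and Section 10.5.2 asks for a reasonable possibility of causation. Neither mentions duration. A long fall that starts on the infusion can meet the Section 10.3 test while Section 5.6 points the investigator to reperfusion.

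**6. The restart cap.** The two-interval limit sits in the quick-recovery paragraph. The slow-recovery paragraph has none, and the text does not say whether those holds count toward it or whether a subject who has used the cap may restart by the slow route. Total dose is bounded: 4 × 30 + 2.2 × 60 = 252 mL, and 252 × 0.16 = 40.3 mg, consistent with the stated 250 mL and 40 mg bag. The 1-hour clause may also bound late dosing. Its scope is unclear, because the uninterrupted schedule itself lasts 30 + 60 = 90 minutes from just before first-lung reperfusion.

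**7. Illustration of scale at n = 8 (Clopper-Pearson 95% intervals).** Moving one subject's event out of a drug-attributed category changes 1/8 (12.5%; 0.3 to 52.7%) to 0/8 (0%; 0 to 36.9%). The plan defines no such rate, so this shows only how sensitive a count of 8 would be.

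**The case against.** The strongest reply is that little depends on these sentences. Much of that stands.

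- **Reporting.** A reader might infer that hypotension assigned to reperfusion goes unreported, since Section 10.3 exempts events expected in transplant care. The documents do not support this. Its examples are infection, rejection and organ failures. Hypotension is named separately as expected from the intervention, and Section 10.3 requires it to go to the sponsor within 5 days.
- **Lost data.** Section 10.5.2 records events regardless of suspected cause, Section 5.8 records all potential adverse events, and Section 5.7.2 takes MAP every minute during the infusion. The endpoint is measured MAP.
- **Overdose.** Both routes hold the drug and require MAP within 10% of baseline before restart, and the bag limits the total.
- **A binding rule.** A reader might take Section 5.6 to attribute a fall to the drug only if it reverses within 10 minutes. The wording for long falls is softer, quick and prolonged are not defined, and formal causality stays with the investigator. Section 10.5.2 also allows a finding of unknown but not related, so a long fall is not automatically drug-related under Section 10.
- **Pharmacology.** The 42 minutes is a plasma figure, and the pressure effect may wear off faster.

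What remains is a presumption about cause with no stated support, inside the section that governs dosing during the primary safety measurement, and a cap that covers only one route.

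**Conclusion.** The point holds as a problem of causality classification and restart consistency. Section 5.6 presumes that duration separates drug from reperfusion, and the documents do not support that. With the stated half-life, 85% of the level remains after the hold. Recovery of a 20% fall within 10 minutes would need a steep effect relation (power about 4.2), fast redistribution of about 41% of the level, or an effect half-life of 10 minutes or less. This is an inference resting on one-compartment decay and an assumed level-to-MAP relation. The mismatch with Section 10 and the one-sided cap need no pharmacokinetic assumption.

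The size of any misclassification cannot be estimated, because the documents give neither the frequency of falls nor the offset time, and hemodynamic support blurs the direction. A change is worth making because it costs almost nothing and removes an avoidable bias from a safety study of 8 subjects without a control.

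**What to change.** 1. Delete the two attribution sentences in Section 5.6. State instead that every MAP fall of more than 20% starting during the infusion, or in the following hour of MAP monitoring already planned in Section 5.7.2, is assessed under Sections 10.3 and 10.5.2 whatever its duration.
2. State that holds by either route count toward the existing two-interval cap.
3. Report the number of the 8 subjects with any such fall, whatever the attributed cause. List each event with its start, depth, duration, pressor or fluid change, and dose delivered.

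The cost is a few sentences and one listing, with no added samples, subjects or monitoring. There are two downsides. Some true reperfusion hypotension will be counted as possibly drug-related, which may overstate the drug's rate; in a first safety study in this population that is the safer error, and the listing lets readers judge each event. A shared cap may also end dosing early and reduce pharmacokinetic data in a few subjects. If the sponsor prefers separate caps to protect exposure, the text should say so and give the slow-recovery route its own number.
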